1.1 Trial information

This is a 26-week randomised, parallel, two-arm, open-label, multi-centre trial comparing the efficacy and safety of liraglutide 1.8 mg/day to liraglutide 0.9 mg/day in Japanese subjects with T2DM. The liraglutide 1.8 mg/day treatment arm will be continued for a total of 52 weeks after randomisation for monitoring of safety and glycaemic control over 52 weeks. Refer to the protocol for further details.

1.2 Scope of the statistical analysis plan

This Statistical Analysis Plan (SAP) is based on the statistical analyses of NN2211-4174 as planned in the trial protocol.

Changes to the statistical methods proposed in this SAP and the reason for the change must be reported in the clinical trial report (CTR).

This SAP is based on the protocol version 3.0 (Dated 10 September 2015).

2 Endpoints

2.1 Primary endpoint

Change from baseline in HbA1c after 26 weeks of treatment

2.2 Secondary endpoints

2.2.1 Secondary efficacy endpoints

- Responder for HbA1c after 26 weeks of treatment (Yes/No):
 - HbA1c < 7.0% (53 mmol/mol)*
 - HbA1c ≤ 6.5% (48 mmol/mol)*
 - HbA1c < 7.0% without weight gain*
 - HbA1c < 7.0% without treatment emergent severe or blood glucose (BG) confirmed symptomatic hypoglycaemic episodes*
- Change from baseline after 26 weeks of treatment in:
 - Self-Measured Blood Glucose (SMBG) 7-point profile

- 7-point profile (individual points in the profile)*
- Mean of 7-point profile*
- Mean of postprandial increments (from before meal to 90 min after for breakfast, lunch and dinner). The mean increment over all meals will be derived as the mean of all available meal increments.*
- Fasting plasma glucose (FPG)*
- Waist circumference*
- Body weight*
- Body mass index (BMI)*
- Blood pressure (systolic and diastolic)*
- Fasting C-peptide, fasting insulin, fasting glucagon, proinsulin, proinsulin/insulin, HOMA-B, HOMA-IR after 26 weeks of treatment*
- Fasting lipid profile (total cholesterol, low density lipoprotein cholesterol [LDL cholesterol], high density lipoprotein cholesterol [HDL cholesterol], very low density lipoprotein cholesterol [VLDL cholesterol], triglycerides, and free fatty acids) after 26 weeks of treatment*

2.2.2 Secondary safety endpoints

- Number of treatment emergent adverse events during 26 weeks of treatment*
- Number of treatment emergent severe or BG confirmed symptomatic hypoglycaemic episodes during 26 weeks of treatment*
- Number of treatment emergent nocturnal severe or BG confirmed symptomatic hypoglycaemic episodes during 26 weeks of treatment*
- Number of treatment emergent hypoglycaemic episodes according to ADA definition during 26 weeks of treatment*
- Change from baseline after 26 weeks of treatment:
 - Clinical evaluations:
 - Physical examination

- Eye examination
- Electrocardiogram (ECG)
- Pulse*
- Laboratory assessments:
 - Biochemistry
 - Haematology
 - Calcitonin

The above mentioned primary endpoint, secondary efficacy endpoints and secondary safety endpoints will also be evaluated separately for 52 weeks of treatment.

* Key secondary endpoint prospectively selected for disclosure (e.g. clinicaltrials.gov and EudraCT)

Please note that following endpoints are also selected for disclosure.

- Change from baseline in HbA1c after 52 weeks of treatment
- Responder for HbA1c after 52 weeks of treatment (Yes/No):
 - HbA1c < 7.0% (53 mmol/mol)
- Change from baseline in body weight after 52 weeks of treatment
- Number of treatment emergent adverse events during 52 weeks of treatment

3 Statistical considerations

Novo Nordisk will analyse and report data from all sites together.

All analyses of efficacy and safety endpoints will be based on the full analysis set (FAS). All efficacy endpoints will be summarised using the FAS and safety endpoints will be summarised using the safety analysis set (SAS).

The impact of protocol deviations and outliers may be investigated further in sensitivity analyses if deemed relevant.

Unless otherwise specified, all continuous measurements will be summarised descriptively at each visit by treatment using all observed data. Descriptive statistics will be presented based both on observed and last observation carried forward (LOCF) imputed data. Endpoints that are analysed untransformed and endpoints that are not formally analysed are summarised by the arithmetic mean, standard deviation (SD), median, and minimum and maximum value. Endpoints that are analysed log-transformed are supplemented with the geometric mean and coefficient of variation (CV). CV is calculated as $\sqrt{\exp(s^2) - 1}$ where s^2 is the SD of log-transformed values.

Unless otherwise specified, laboratory values below the lower limit of quantification (LLOQ) will be set to $\frac{1}{2}$ LLOQ.

For measurements over time, mean values will be plotted to explore the trajectory over time. LOCF imputed data will be used as the basis for plotting data, if not otherwise specified. For endpoints that are analysed log-transformed, the geometric mean values will be plotted.

An analysis of covariance (ANCOVA) model will be applied for the primary endpoint and continuous secondary endpoints after 26 weeks of treatment. The model includes treatment as a fixed effect and the corresponding baseline value as a covariate. In the following, this model will be referred to as the standard ANCOVA model.

Presentation of results from a statistical analysis will include the estimated mean treatment effects (Least Square Means [LSMeans]) for absolute values and change from baseline. In addition, estimated mean treatment difference (or ratio) will be presented together with the two-sided 95% confidence interval and corresponding two-sided p-value. The “obsmargins” option will be used in the “LSMEANS TREATMENT”.ⁱ

Handling of missing data

The expected percentage of missing data is around 10%. In accordance with industry guidanceⁱⁱ endpoints will be assessed at frequent visits and also on subjects who withdraw prematurely. This will facilitate an analysis in accordance with ITT principles. Also, the combined information on frequent outcomes and information on reason for drop-out is assumed to account for the missing data anticipated.

If not otherwise specified, the value from the randomisation visit (Visit 8) will be used as the baseline value. If the value measured at the randomisation visit is missing and the assessment has also been made at an earlier visit, then the non-missing value obtained at the preceding visit closest to Visit 8 will be used as the baseline value.

Missing values (including intermittent missing values) will be imputed using the LOCF method. Subjects without data after randomisation will be included by carrying forward their baseline value. In this trial, sensitivity analyses will be made to examine the robustness of the LOCF method.

Handling of laboratory measurements

A laboratory measurement in which the central laboratory could not guarantee a reliability of data, e.g. measurements with a comment like "Only for reference because of xxxx", will not be used for the summary and statistical analysis.

For laboratory parameters which is required to be measured in a fasting status (fasting plasma glucose, fasting insulin, fasting C-peptide, fasting glucagon, proinsulin and all lipids), the measurements in a non-fasting status will not be used for the summary and statistical analysis.

Handling of retest data

If more than one measurement exists at a visit after exclusion of non-fasting values for the fasting parameters or non-reliable laboratory data, the first one is chosen.

Visit reallocation

The following basic ideas are followed:

- 1) Visit reallocation is not applicable for assessments performed before date of first dosing of the randomised treatment.
- 2) Visit reallocation is only applicable for non-missing assessments. Hence, if an assessment is missing or treated as missing it cannot be reallocated to a different visit.
- 3) Any scheduled measurement (observed or missing), except the end of trial visit for the premature discontinuation (EOTpd), cannot be relocated to another visit.
- 4) Observed unscheduled measurements can only substitute preceding and adjacent scheduled assessments if these latter measurements were planned to be sampled in fasting conditions but were in fact sampled in non-fasting conditions.

Notice that such a non-fasting record which should have been fasting may or may not be actually missing. Regardless, the non-fasting record will be treated as missing.

- 5) Observed scheduled measurements from EOTpd should replace
 - a. the adjacent earlier scheduled assessments from the preceding visit, in case this assessment is missing
 - b. the later adjacent scheduled missing assessment from the succeeding visit in case the adjacent earlier scheduled assessment from the preceding visit is not missing.

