3.2 Definition of analysis sets

The following analysis sets are defined in accordance with the ICH-E9 guidance.ⁱⁱⁱ

- **Full Analysis Set (FAS):** includes all randomised subjects. The statistical evaluation of the FAS will follow the intention-to-treat (ITT) principle and subjects will contribute to the evaluation “as randomised”.
- **Safety Analysis Set (SAS):** includes all subjects receiving at least one dose of liraglutide. Subjects in the safety analysis set will contribute to the evaluation “as treated”.

Subjects who are lost to follow up and where no exposure information of liraglutide is available will be handled as unexposed.

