3.4.2 Safety endpoints

Adverse events

AEs will be coded using the most recent version of the Medical Dictionary for Regulatory Activities.

A treatment emergent adverse event (TEAE) is defined as an event that has onset date on or after the first day of IMP administration and no later than seven days after the last day on IMP. If the event has onset date before the first day of IMP administration and increases in severity during the treatment period and until 7 days after the last drug date, then this event should also be considered as a TEAE. Here the first day of IMP administration is defined as the first day of exposure to liraglutide.

AEs will be summarised descriptively for each of the following periods separately:

- The run-in period: TEAEs with an onset date on or after the first day of exposure to liraglutide and before the date of randomisation will be reported as part of the run-in period. For the run-in failure subjects, AEs with an onset date on or after the first day of exposure to liraglutide and no later than seven days after the last day of liraglutide treatment will be reported as part of the run-in period.
- The 26 week treatment period: TEAEs with an onset date on or after the date of randomisation and no later than seven days after Visit 16 (EOT26) will be reported as during 26 weeks of treatment. For subjects in the liraglutide 0.9 mg arm as well as for subjects in both arms who withdrew from the trial during 26 weeks of treatment, TEAEs with an onset date on or after the date of randomisation and no later than seven days after the last day of liraglutide treatment will be reported as part of 26 weeks of treatment.
- The 52 week treatment period: For the liraglutide 1.8 mg arm all TEAEs with an onset date on or after the date of randomisation will be reported as during 52 weeks of treatment.

For each of the above periods, AE data will be displayed in terms of the number of subjects with at least one event (N), the percentage of subjects with at least one event (%), the number of events (E) and the event rate per 100 years of exposure (R).

Summaries of AEs and of serious AEs will be presented as an overview including all AEs, serious AEs, number of deaths, AEs by severity, AEs by relation to treatment and AEs of special interest including AEs leading to withdrawal for each period.

Furthermore separate summary tables for each period will be presented based on system organ class and preferred terms for:

- All AEs
- Serious AEs

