For each of the periods listed above, data on hypoglycaemic episodes are presented above in terms of the number of subjects with at least one event (N), the percentage of subjects with at least one event (%), the number of events (E) and the event rate per 100 years (R). Separate summaries are made for severe or BG confirmed symptomatic hypoglycaemic episodes, nocturnal severe or BG confirmed symptomatic hypoglycaemic episodes and the ADA classification of hypoglycaemia.

The number of hypoglycaemic episodes during 26 weeks of treatment will be analysed separately for each endpoint listed above using a negative binominal regression model with a log-link function and the logarithm of the time period in which a hypoglycaemic episode is considered to be part of the 26 week treatment period as offset. The model will include treatment as factor. For each endpoint, the analysis will be performed only if the number of episodes observed is adequate for convergence of the model fit.

Pulse

Pulse will be summarized descriptively.

Clinical evaluations (physical examination, eye examination and ECG)

Eye examination (fundoscopy/fundus photography) and ECG findings will be summarised descriptively, including:

- summaries for each visit
- shift table from baseline to after 26 weeks of treatment and after 52 weeks of treatment

Any findings in the physical examination evaluation at screening will be presented as listings. Any clinically significant deterioration of a pre-existing condition after the screening visit, as well as any new clinically significant findings will be recorded as adverse events.

Laboratory assessments

All laboratory parameters will be summarised descriptively.

The following tables will be presented based on both observed and LOCF imputed data:

- Shift tables from baseline to after 26 weeks of treatment and after 52 weeks of treatment
- Proportion of subjects with measurements outside reference range by treatment and week.

Laboratory values will be presented graphically as box plots by treatment and week.

For each laboratory parameter, individual values outside the reference ranges (abnormal values) will be listed.

For lipase and amylase the following rule will apply in the evaluation of the result:

- If the amylase or lipase baseline (at screening) value is $> 3 \times \text{UNR}$ this information is to be recorded as medical history for that subject.

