The purpose of the calcitonin analysis is to evaluate longitudinal changes in calcitonin, with main focus on subjects who develop persistently high levels of calcitonin during the trial.

Calcitonin will be displayed in terms of the number of subjects (N), the percentage of subjects (%) and the incidence rate per 100 years of exposure (R). The following criteria are defined for tabulations:

Persistent (all post baseline measurements)

- From $< \text{UNR}$ to persistently $\geq \text{UNR}$
- From $< \text{UNR}$ to persistently $\geq 1.5 \text{ UNR}$
- From $< \text{UNR}$ to persistently $\geq 20 \text{ ng/L}$
- From $< \text{UNR}$ to persistently $\geq 50 \text{ ng/L}$
- From $< 20 \text{ ng/L}$ to persistently $\geq 20 \text{ ng/L}$
- From $< 50 \text{ ng/L}$ to persistently $\geq 50 \text{ ng/L}$

Incidental (at least one post baseline measurements)

- From $< \text{UNR}$ to $\geq \text{UNR}$
- From $< \text{UNR}$ to $\geq 1.5 \text{ UNR}$
- From $< \text{UNR}$ to $\geq 20 \text{ ng/L}$
- From $< \text{UNR}$ to $\geq 50 \text{ ng/L}$
- From $< 20 \text{ ng/L}$ to $\geq 20 \text{ ng/L}$
- From $< 50 \text{ ng/L}$ to $\geq 50 \text{ ng/L}$

The distribution of all calcitonin measurements across treatment groups and time will be shown with histograms and corresponding cumulative plots for actual levels of calcitonin and change from baseline. The plots will be presented by treatment group (using EOT measurement - LOCF) and within treatment group by week. Plots will be done by gender.

Summaries tables of calcitonin continuous measurements, will include number and percentage of observations $<$ and \geq LLOQ, minimum, Q25, median, Q75 and maximum. Summaries will be presented for all subjects and by gender.

Longitudinal changes for subjects with calcitonin levels $\geq 20 \text{ ng/L}$ will be plotted (longitudinal plots). The plots will be done by treatment and gender. They will be done for subjects in the persistent and incidental categories, separately.

A listing of subjects with at least one post baseline value $\geq 20 \text{ ng/L}$ will be done. The listing will include age, gender, calcitonin measurements over time and AE history (including preferred term, onset and stop dates).

4 Changes to the statistical analyses planned in the protocol

The following changes from the protocol are implemented in this SAP.

Full analysis set

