In the protocol, it was stated that “In exceptional cases, subjects may be eliminated from the full analysis set. In such cases the elimination will be justified and documented.”. Since it is technically difficult to keep the statisticians and programmers blinded before database lock in this trial design, it is deleted in order to minimise the potential bias by excluding the subjects based on the knowledge of randomised treatment for each subject.

Data handling

The possible data handlings are described in order to minimise the potential bias and the following text in section 17.2 in the protocol section was deleted.

Before data are released for statistical analysis, a review of all data will take place to identify protocol deviations that could potentially affect the results. Any decision to exclude any subject or observation from the statistical analysis is the joint responsibility of the members of the study group. The subjects or observations to be excluded, and the reasons for their exclusion must be documented and signed by those responsible before database lock. The subjects and observations excluded from analysis sets, and the reason for this, will be described in the clinical trial report.

The following changes from SAP version 1 are implemented in SAP version 2.

Endpoints section is created according to the protocol and endpoints selected for disclosure are updated.

Sensitivity analysis

As a sensitivity analysis for the primary endpoint, a pattern mixture model approach using multiple imputation is added.

Blood pressure (systolic and diastolic)

Statistical analysis is added for change from baseline in systolic blood pressure and diastolic blood pressure after 26 weeks of treatment as well as other efficacy secondary endpoints.

Safety analysis set

In the protocol, it was stated that the Safety Analysis Set “includes all subjects receiving at least one dose of randomised treatment”. In order to clarify that all adverse events occurring after initiation of treatment with liraglutide (including during the run-in phase) will be reported appropriately, this has been updated to state “includes all subjects receiving at least one dose of liraglutide”. Deletions are ~~struck through~~ and new text is in **bold**.

- Safety Analysis Set (SAS): includes all subjects receiving at least one dose of ~~randomised treatment~~**liraglutide**. Subjects in the safety analysis set will contribute to the evaluation “as treated”.

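### By default the calcitonin categories and laboratory shift tables start from Visit 8, after run-in liraglutide, so where a sample exists by then a threshold first crossed in the run-in is not counted as a rise

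*SAP*

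**What the plan says.** **Baseline.** SAP section 3, Handling of missing data: "If not otherwise specified, the value from the randomisation visit (Visit 8) will be used as the baseline value". If that value is missing and an earlier one exists, "the non-missing value obtained at the preceding visit closest to Visit 8 will be used as the baseline value".

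**Liraglutide before randomisation.** Section 3.4.2 defines a run-in reporting period made up of "TEAEs with an onset date on or after the first day of exposure to liraglutide and before the date of randomisation". Section 3.2 defines the safety analysis set so that it "includes all subjects receiving at least one dose of liraglutide". Section 4 gives the reason for that definition, which is new in version 2: to make clear that "all adverse events occurring after initiation of treatment with liraglutide (including during the run-in phase) will be reported appropriately". The same revision moved the treatment-emergent definitions for adverse events and hypoglycaemia to first liraglutide exposure.

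**Calcitonin (section 3.4.2).** The analysis has its "main focus on subjects who develop persistently high levels of calcitonin during the trial". There are six persistent and six incidental criteria. Each pairs a starting condition (baseline below UNR, 20 or 50 ng/L) with a target. Persistent means that all post-baseline values reach the target; incidental means that at least one does. There is also "A listing of subjects with at least one post baseline value" of 20 ng/L or more. No calcitonin-specific baseline is named.

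**Laboratory assessments (section 3.4.2).** Shift tables run from baseline to 26 and to 52 weeks, again with no separate baseline. The section also plans by-week proportions outside the reference range and a listing of individual abnormal values.

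**The concern.** The calcitonin section sets out to find high levels that develop in the course of the trial. The run-in is part of the trial, and it is when subjects start the drug. If the reference value is taken at the end of the run-in, a subject who was low before liraglutide and high by Visit 8 is treated as having started high. For the threshold crossed, the subject cannot enter the matching row however long the rise lasts. In a shift table, high-to-high reads as a pre-existing abnormality.

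The SAP is also uneven here. Adverse events and hypoglycaemia have a run-in period counted from the first dose; calcitonin categories and laboratory shifts have none. A calcitonin increase reported as an adverse event in the run-in would be treatment emergent, while the laboratory categories would show no rise for it.

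At stake is the completeness of the descriptive safety picture for liraglutide overall. The randomised comparison of the two doses is not at stake.

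**Working it through.** The SAP gives no figure to reproduce, so the check applies its own calcitonin criteria to example subjects.

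**Inputs from the SAP (section 3.4.2).** Six rows, written as (start *a*, target *b*): (UNR, UNR), (UNR, 1.5 UNR), (UNR, 20), (UNR, 50), (20, 20), (50, 50), in ng/L where numeric.

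**Assumed inputs.** UNR is not given; 6, 8.5 and 12 ng/L were tried. The pre-liraglutide (screening) value is 3 ng/L. There is a Visit 8 sample and there are three later ones.

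**Rule.** A subject enters row (*a*, *b*) if baseline < *a* and all (persistent) or at least one (incidental) of the post-baseline values are ≥ *b*.
- Visit 8 version: baseline is the Visit 8 value; only later values are post-baseline.
- Pre-liraglutide version: baseline is the screening value; Visit 8 and later values are post-baseline.

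**Results** (rows entered out of 6, persistent / incidental; the same for all three assumed UNR values):

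| Screening → Visit 8 → later | Visit 8 baseline | Pre-liraglutide baseline |
|---|---|---|
| 3 → 1.6 × UNR → unchanged | 0 / 0 | 2 / 2 |
| 3 → 25 → 25, 26, 25 | 0 / 0 | 4 / 4 |
| 3 → 55 → 55, 56, 55 | 0 / 0 | 6 / 6 |
| 3 → 25 → 55, 56, 55 | 1 / 1 (50, 50) | 4 / 6 |
| 3 → 1.2 × UNR → 22, 22, 22 | 1 / 1 (20, 20) | 1 / 4 |

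**Second line by hand.** With Visit 8 at 25, the baseline is not below UNR (at most 12) and not below 20, so five rows are closed. Row (50, 50) is open, but the later values never reach 50. Result: 0. From a baseline of 3 all six rows are open. Values of 25 or 26 meet the targets UNR, 1.5 UNR (at most 1.5 × 12 = 18), 20 and 20, but not the two targets of 50. Result: 4.

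**What the last two lines show.** A further rise past 20 or 50 ng/L after Visit 8 is still counted in the row that starts below that level. The four rows starting below UNR stay closed to anyone at or above UNR at Visit 8. These lines also show the price of the alternative: once the Visit 8 value counts as post-baseline, the fourth subject leaves the persistent (50, 50) row and the fifth leaves the persistent (20, 20) row, because their Visit 8 values are below the target.

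**Shift tables.** The first three subjects are above UNR at Visit 8 and later. They fall in high-to-high from Visit 8, and in normal-to-high from a normal pre-liraglutide value.

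**Run-in failures.** They have taken liraglutide, so they are in the safety set, but they have no Visit 8. If the fallback is read as applying to them, their last value closest to where Visit 8 would have been becomes baseline and nothing follows it. If it is not, they have no baseline. Either way they have no clear post-baseline value for the categories or for the 20 ng/L listing.

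**The case against.** The strongest objection is that the consequence depends on a sampling schedule that the SAP leaves to the protocol. If a parameter's last sample before randomisation was taken at screening, the fallback makes that pre-liraglutide value the baseline and the problem does not arise for it. This stands, and the point is conditional on a sample at Visit 8 or earlier on run-in drug.

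Second, Visit 8 is the proper baseline for comparing 1.8 with 0.9 mg/day, and the version 2 change was justified in terms of adverse events, not laboratory values. This also stands. It is a reason to keep Visit 8, but not to have only Visit 8 when the stated interest covers the whole trial.

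Three stronger readings are tempting but not supported:
- *Run-in rises disappear from the report.* They do not. Abnormal values are listed for every laboratory parameter, by-week proportions outside the reference range are shown, and a randomised subject with any later value of 20 ng/L or more is in the calcitonin listing whatever the baseline.
- *The tables conceal an effect of starting liraglutide.* The run-in has no comparator, and ordinary within-subject variation alone moves some subjects across a threshold. Neither baseline can attribute a rise to the drug.
- *The SAP contradicts itself because its amylase and lipase rule takes baseline at screening.* That rule defines its own term for recording medical history, which the general baseline rule allows.

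**Conclusion.** The point holds in a limited form. By default, the calcitonin rows and laboratory shift tables start from a value taken after run-in liraglutide. Where such a sample exists, a threshold first crossed in the run-in is not counted in the row for that threshold and appears as high-to-high in the shift table. For a subject whose run-in rise is sustained, the difference is 0 rows against 2, 4 or 6 of 6, depending on the level reached. Run-in failures are in the safety set without a usable post-baseline value.

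The size is given per example subject only. The SAP provides no sampling schedule, no UNR and no calcitonin distribution, so the number of subjects affected cannot be estimated from it. The example counts rest on the assumed values and on a Visit 8 sample being taken. The tables concerned are descriptive; no hypothesis test, efficacy result or trial procedure changes. This is a worthwhile low-cost improvement, not a flaw that undermines the plan.

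**What to change.** 1. Keep Visit 8 as baseline for the 1.8 versus 0.9 mg/day presentation, and say so in the table titles.
2. Add supplementary calcitonin categories, the 20 ng/L listing and laboratory shift tables for the safety analysis set, with the last value before first liraglutide exposure as baseline. Count all later values as post-baseline: run-in, Visit 8, after randomisation, and those of run-in failures.
3. Show the supplementary persistent rows beside the Visit 8 version, because counting run-in and Visit 8 values as post-baseline removes late risers from the persistent rows.
4. If a parameter has no pre-liraglutide sample, state in the table title that change is from a value on liraglutide.

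**Cost.** A few sentences in the SAP and one further set of descriptive outputs from whatever pre-dose samples were taken. There is more to read, and the incidence figure may be less favourable. The added tables should carry a note that the run-in has no comparator, so they describe rises and do not attribute them.
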